The study was originally powered based on the API ADAD Composite Cognitive Test Battery total score. However, due to concerns about learning effects and general lack of sensitivity to change in a cognitively normal population, before study unblinding, the Sponsor performed a blinded power analysis on the original primary endpoint API ADAD Composite Cognitive Test Battery Total Score and the secondary clinical endpoints. The Sponsor decided to promote the FCSRT Cueing Index from a secondary endpoint to part of a primary endpoint family (along with the API ADAD Composite) due to its favorable statistical properties and clinical relevance as a sensitive measure of episodic memory dysfunction—the hallmark of emerging symptomatic AD and the most commonly observed, early, and consistent neuropsychological marker of AD. In the SAP, the Sponsor will provide details of the blinded power analysis along with the evidence of type I error control.

INTERIM ANALYSIS

To adapt to information that may emerge during the course of this study, the Sponsor may choose to conduct one or more interim analyses. Sites are to be informed prior to an interim analysis. Below are the specifications to ensure the study continues to meet the highest standards of integrity when an optional interim analysis is executed.

If an interim analysis is conducted, the Sponsor will remain blinded. The interim analysis will be conducted by an external statistical group and reviewed by the iDMC. Interactions between the iDMC and Sponsor will be carried out as specified in the iDMC Charter.

The decision to conduct the optional interim analysis, along with the rationale, timing, and statistical details for the analysis, will be documented in the SAP. The iDMC Charter will be updated to document potential recommendations the iDMC can make to the Sponsor as a result of the analysis (e.g., stop the study for positive efficacy, stop the study for futility), and the iDMC Charter will also be made available to relevant health authorities.

If there is a potential for the study to be stopped for positive efficacy as a result of the interim analysis, the type I error rate of the primary analysis will be controlled to ensure statistical validity is maintained. If the study continues beyond the interim analysis, the critical value at the final analysis would be adjusted accordingly to maintain the protocol-specified overall type I error rate, per standard Lan-DeMets methodology.

ANALYSES FOR STUDY PERIOD B

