3. SAMPLE SIZE DETERMINATION

This study will enroll up to 300 participants: up to 200 participants will be enrolled in the carrier cohort and up to 100 participants will be enrolled in the non-carrier cohort. Participants in the carrier cohort will be randomized in a 1:1 randomization ratio to active treatment or placebo. The study was initially powered to compare the mean change from baseline over 260 weeks in the API ADAD Composite Cognitive Test total score between the active treatment group and the placebo group. Assuming a 25% dropout rate with use of two-sided testing at the overall 0.05 level, a placebo group coefficient of variation of 65% for the Week 260 change scores ($= 100\% \times$ standard deviation of

[figure not shown]
placebo participant change scores/mean of placebo participant change scores) and 100 participants per arm, the study will have at least 80% power to detect a true effect of 30% reduction of the mean decline in the API ADAD Composite Cognitive Test total score in the placebo group using a t-test. Participants in the non-carrier cohort will all receive placebo and will be included in the study in order to maintain the genotype blind.

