5.3.3 Main Analytical Approach for Primary Endpoint Family

The primary analysis on both primary endpoints will be performed using a RCRM (Richeldi et al. 2014; Flaherty et al. 2019; Hu et al. 2021) with a missing at random (MAR) assumption. This model will include all observations, including baseline scores as the response variable. The RCRM will include the randomization stratification factors described in Section 5.3 as fixed effects with an intercept, and will include the categorical treatment groups as interaction terms with time; *stratification factor(s) may be removed from the model if there is risk of non-convergence or sparse strata (in case*

of non-convergence, stratification factors will be removed in the order of the smallest number of observations in any cell caused by that stratification factor).

Participant-level random intercept and random slope are also included in the model, where an unstructured covariance between the random intercept and random slope is assumed. The RCRM is constructed as follows:

$$Y_{ij} = \alpha + (\text{Randomization Factors})_i + u_{0i} + (\beta + \beta_x l_{x,i} + u_{1i}) t_{ij} + \varepsilon_{ij}$$

where Y_{ij} is the score for participant i at visit j ; t_{ij} is the duration in the unit of year after first drug intake for participant i at visit j ; $l_{x,i} = 1$ if participant i in a *PSEN1* E280A mutation carrier is in the crenezumab mITT group, and $l_{x,i} = 0$ if participant i is a *PSEN1* E280A mutation carrier is in the placebo mITT group; u_{0i} and u_{1i} are random intercept and random slope, respectively, for the i^{th} participant; ε_{ij} is the random error for the i^{th} participant at visit j . The crenezumab treatment effect on the rate of change is quantified by β_x ; the 95% CI and p-value for crenezumab treatment effect will be presented. The crenezumab treatment effect compared with the placebo group on the relative reduction (RR) scale is calculated as $-\beta_x/\beta \times 100\%$; its estimate will also be presented; its 95% CI using bootstrap approach will also be provided.

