To understand the treatment effect on each component of one of the primary endpoints (API ADAD Composite Cognitive Test total score), the same primary analysis model will be run on each component. The 95% CIs and p-values for the treatment effect estimator will be presented. A forest plot will be made.
- To explore whether decline accelerates or decelerates, a quadratic RCRM where leading t^2 terms (treatment and time 2 interaction terms and random quadratic term) are added to the primary analysis model. The covariance matrix of $\{u_{0i}, u_{1i}, u_{2i}\}$ is assumed to be unstructured and all random effect terms are assumed to be independent of the pure error term. Specifically, this model is written as:

$$Y_{ij} = \alpha + (\text{Randomization Factors})_i + u_{0i} + (\beta + \beta_x I_{x,i} + u_{1i})t_{ij} + (\theta + \theta_x I_{x,i} + u_{2i})t_{ij}^2 + \epsilon_{ij}.$$

All statistical inferences as in the primary analysis model along with the point estimates of θ_x and 95% CI will be presented.

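### The supplementary quadratic RCRM reports βₓ and −βₓ/β as the treatment effect, but with t² terms these apply only at first dose and are not the annualized effect

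*SAP*

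**What the plan says.** SAP 5.3.3 fits a linear RCRM in which t "is the duration in the unit of year after first drug intake for participant" i. "The crenezumab treatment effect on the rate of change is quantified by" the coefficient βₓ, for which a p-value and a confidence interval at the 95% level are planned. The relative reduction is defined there as −βₓ/β × 100%, with a bootstrap CI. SAP 5.3.2 gives the population summary as the arm difference in annualized rate of change.

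SAP 5.3.5 lists a further supplementary analysis: "To explore whether decline accelerates or decelerates, a quadratic RCRM where leading" t² terms are added, namely θt², a treatment term θₓt² and a random quadratic term. Its output is "All statistical inferences as in the primary analysis model along with the point estimates of" θₓ and a 95% CI. For this model the SAP names no contrast at a stated time, no average-slope contrast, no redefined relative reduction and no joint test of βₓ and θₓ.

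**The concern.** Once t² enters the model, βₓ keeps its symbol but changes its meaning. In the linear model it is the yearly treatment difference. In the quadratic model it is the slope difference at the moment of first dosing, and β is the placebo slope at that moment. The carried-over p-value and relative reduction therefore answer a question about day one of treatment.

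The model is meant for trajectories that bend. If the benefit builds up over time, the quantity labelled as the treatment effect leaves that benefit out. A reader who compares the quadratic result with the primary result could take a 0% or negative relative reduction as evidence against the drug.

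**Working it through.** **The plan's own figure.** SAP 5.3.5 states no number. The nearest is the power statement in SAP section 3: "Assuming a 25% dropout rate with use of two-sided testing at the overall 0.05 level", CV 65%, 100 per arm, 30% reduction. With 75 completers per arm, the standardized effect is 0.30/0.65 = 0.4615. Then 0.4615 × √(75/2) = 2.826 and Φ(2.826 − 1.960) = 80.7% (80.2% with the noncentral t). The stated power of at least 80% is reproduced. It supplies the 75 per arm and the 30% effect used below.

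**Algebra (no assumptions).** In the quadratic model:
- Arm difference at time t: βₓt + θₓt².
- Difference in slope at t: βₓ + 2θₓt. Placebo slope at t: β + 2θt.
- Average annual difference from 0 to T: βₓ + θₓT.

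So βₓ and −βₓ/β describe t = 0 only. If the benefit is proportional to t², βₓ = 0 and the relative reduction is exactly 0%, whatever the variances. Example: placebo −0.2t and benefit 0.012t². At 5 years the benefit is 0.012 × 25 = 0.30 against a decline of 1.0, a 30% reduction. The planned readout is 0%. The 5-year version is −(0 + 5 × 0.012)/(−0.2) = 30%.

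**Expected fits at the flowchart visits.** Inputs are composite visits at Weeks 0, 12, 24, 52, 76, 104 and so on to 260 or 416 (Protocol Appendices 1 and 2), 75 per arm, and a 5-year placebo decline scaled to 1. The documents give no variance components, so two sets were assumed (SDs of intercept, slope, quadratic term and residual): A = 0.5, 0.12, 0.01, 0.2 and B = 0.5, 0.10, 0.02, 0.4. Placebo is either linear (−0.2t) or accelerating (−0.1t − 0.02t²). The true 5-year reduction is 30% in every row. Ranges cover sets A and B.

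| True benefit | Visits to | βₓ | −βₓ/β, linear placebo | −βₓ/β, accelerating placebo | 5-year version |
|---|---|---|---|---|---|
| 0.012t² | 5 or 8 y | 0 | 0% | 0% | 30% |
| 0.10(t − 2), from year 2 | 5 y | −0.0195 | −10% | −20% | 32% |
| 0.10(t − 2), from year 2 | 8 y | +0.023 to +0.025 | 12% | 23% to 25% | 30% |
| 0.15(t − 3), from year 3 | 5 y | −0.062 to −0.064 | −31% to −32% | −61% to −64% | 28% |
| 0.15(t − 3), from year 3 | 8 y | −0.021 | −10% to −11% | −21% | 28% |

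For onset at year 3 with 5 years of visits, z for βₓ is −2.25 in set A, nominally significant in the wrong direction, and −1.45 in set B. In the t² row, the test of βₓ rejects 5% of the time.

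**Precision.** Assume 84 per arm (the figure in the SAP Appendix 2 simulation), follow-up spread over 5 to 8 years, residual SD 4 and slope SD 0.5, 1.0 or 1.5. The SE of βₓ rises from the linear to the quadratic model as follows: 0.110 to 0.271 (ratio 2.46), 0.174 to 0.305 (1.75) and 0.245 to 0.351 (1.43). The SE of βₓ + 5θₓ is 0.119–0.142, 0.179–0.195 and 0.249–0.260, which is 1.02 to 1.29 times the linear SE.

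**The case against.** The strongest reply is that the full planned output would not hide a late benefit.

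- θₓ and its 95% CI are reported in the same sentence. They answer the stated question of whether decline speeds up or slows down.
- SAP 5.3.4 specifies an MMRM with a treatment difference, CI and p-value at each timepoint, with no assumption about shape.
- The linear RCRM stays the primary analysis. With the t² benefit and 5 years of visits it gives a relative reduction of 28% to 30%.
- The quadratic model is supplementary, outside the alpha-controlled procedure, and carries no decision rule.

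All of this stands, and it limits the importance of the point. It does not cure it. The SAP promises a CI for θₓ but no p-value, and θₓ alone is not a treatment effect at any time. Its CI is also not sure to exclude zero. For the t² benefit the chance that it does is 28% in set B with 5 years of visits, 81% in set B with 8 years, and close to 100% in set A with 8 years.

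Two stronger readings are tempting. One is that the protocol predicts an early practice gain, so that β would be positive and the ratio meaningless. With a placebo slope of +0.04 per year at first dose and a constant benefit of 0.06, the ratio would indeed be −0.06/0.04 = −150%. But Protocol 4.10.8 records only a change made "due to concerns about learning effects and general lack of sensitivity to change in a cognitively normal population". It gives no trajectory, and Protocol Appendix 7 says the composite was chosen for its sensitivity once practice effects are controlled for. The other is that any late benefit is reported with the wrong sign. The table contradicts this: onset at year 2 with visits to 8 years gives an attenuated positive value, and the common-close design takes many participants past 5 years.

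**Conclusion.** The point holds in limited form. As written, the quadratic RCRM's treatment effect, p-value and relative reduction describe first dosing and not the annualized effect. This follows from the algebra alone, as does the 0% result for a benefit proportional to t². The wrong sign is a possibility that depends on effect shape, follow-up and assumed variance components. It appeared for onset at year 3 with 5 or 8 years of visits, and for onset at year 2 only when visits stopped at 5 years.

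The primary test, the MMRM and the type I error control are unaffected. A reader might infer that the trial could miss a late benefit because of this. The documents do not support that, because other planned outputs would carry it. The error is confined to one supplementary model's headline numbers, but it is worth correcting because those numbers would be set beside the primary result under the same name.

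**What to change.** In SAP 5.3.5, replace the carried-over inferences for the quadratic RCRM with:

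- Treatment effect: the average annual difference over 5 years, βₓ + 5θₓ, with 95% CI and p-value. The Week 260 difference, 5βₓ + 25θₓ, is the same contrast multiplied by 5.
- Relative reduction: −(βₓ + 5θₓ)/(β + 5θ) × 100%, with the bootstrap CI already used for the primary model.
- θₓ with its 95% CI, as planned.
- βₓ, if shown, labelled as the slope difference at first dose.

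A 2-df joint test of βₓ = θₓ = 0 is optional. The cost is one SAP sentence and one contrast statement per endpoint. No new data, model or alpha is needed.

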5.3.5.1 Subgroup Analyses for Primary Endpoints

The following subgroups will be analyzed with respect to the primary endpoints using the same primary analysis. Forest plots will be presented to summarize the results.

The subgroup categories may be combined if there is not enough representation of a specific subpopulation or if the statistical model fails to converge.

- Age (≤ 38 vs. > 38)
- Education (< 9 years vs. ≥ 9 years)
- APOE4 carrier status (carrier vs. non-carrier)
- Baseline CDR zero vs. CDR non-zero
- Amyloid status at baseline (amyloid positive vs. amyloid negative) using a standardized uptake value ratio (SUVr) threshold (*details of the threshold will be prespecified in the biomarker analysis plan*)

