2.4 EXPLORATORY OBJECTIVES

The exploratory objectives for this study are as follows:

- Assess further the effect of crenezumab in preclinical *PSEN1 E280A* mutation carriers on additional clinical measures of efficacy and biological markers of disease that have not been prespecified as primary or secondary endpoints in the SAP
- Explore pharmacogenetic effects, including but not limited to, a person's *APOEε4* carrier status on the active treatment's cognitive, clinical, and adverse effects
- Explore effects of genetic variation, including but not limited to, how genes affect the biology of AD and related disorders and how genes influence biomarker responses
- Examine clinical and biomarker changes in non-carriers and to compare these changes with those seen in carriers treated with placebo
- Relate the treatment's biomarker effects to clinical outcomes and to examine predictive and prognostic utility of baseline characteristics
- Assess the impact of treatment on brain tau load over time, as measured by tau PET imaging in an optional substudy (GN28352-1/BN40199)

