4.10.8 Determination of Sample Size

This study will enroll up to 300 participants: up to 200 participants will be enrolled in the carrier cohort and up to 100 participants will be enrolled in the non-carrier cohort.

Participants in the carrier cohort will be randomized in a 1:1 randomization ratio of active to placebo participants. The study was originally powered to compare the mean change from baseline over 260 weeks in the API ADAD Composite Cognitive Test total score between the crenezumab group and the placebo. Assuming a 25% dropout rate, two-sided testing at an overall 0.05 level, a placebo group CV of 65% for the Week 260 change scores ($=100\% \times$ standard deviation of placebo participant change scores/mean of placebo participant change scores) and 100 participants per arm, the study will have at least 80% power to detect a true effect of 30% reduction of the mean decline in the placebo group.

Participants in the non-carrier cohort will all receive placebo and will be included in the study in order to maintain the genotype blind.

The study was originally powered based on the API ADAD Composite Cognitive Test Battery total score. However, due to concerns about learning effects and general lack of sensitivity to change in a cognitively normal population, before study unblinding, the Sponsor performed a blinded power analysis on the original primary endpoint API ADAD Composite Cognitive Test Battery Total Score and the secondary clinical endpoints. The Sponsor decided to promote the FCSRT Cueing Index from a secondary endpoint to part of a primary endpoint family (along with the API ADAD Composite) due to its favorable statistical properties and clinical relevance as a sensitive measure of episodic memory dysfunction—the hallmark of emerging symptomatic AD and the most commonly observed, early, and consistent neuropsychological marker of AD (Tounsi et al. 1999; Bateman et al. 2012; Caselli et al. 2020) In the SAP, the Sponsor will provide details of the blinded power analysis along with the evidence of type I error control.

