2. STATISTICAL HYPOTHESES

The primary endpoint family consists of 2 endpoints: 1) annualized change on the Alzheimer's Prevention Initiative (API) ADAD Composite Cognitive Test total score and 2) annualized change on Free and Cued Selective Reminding Task (FCSRT) Cueing Index. The type I error is split between testing the treatment effect on the API ADAD Composite Cognitive Test total score ($\alpha=0.04$) and on the FCSRT Cueing Index ($\alpha=0.01$). If at least one of the 2 primary analyses is statistically significant, then the trial is considered positive. The primary endpoint family in the crenezumab arm and placebo arm will be compared among mutation carriers and tested using a random coefficient regression model (RCRM) with the null and alternative hypotheses as follows.

- API ADAD Composite Cognitive Test total score:
 - H_0 : There is no difference in annualized change on the API ADAD Composite Cognitive Test total score between the crenezumab and placebo arms among mutation carriers
 - H_1 : There is a difference in annualized change on the API ADAD Composite Cognitive Test total score between the crenezumab and placebo arms among mutation carriers
- FCSRT Cueing Index:
 - H_0 : There is no difference in annualized change on FCSRT Cueing Index between the crenezumab and placebo arms among mutation carriers.
 - H_1 : There is a difference in annualized change on FCSRT Cueing Index between the crenezumab and placebo arms among mutation carriers.

Details on the type I error control are described in Section [3.1](#).

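### The subgroup analyses of the primary endpoints specify no estimate of how far the treatment effect differs between levels

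*SAP*

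**What the plan says.** SAP 5.3.5.1 names five factors, each with two levels: age, education, APOE4 status, baseline CDR and baseline amyloid status. On method it says "The following subgroups will be analyzed with respect to the primary endpoints using the same primary analysis". On display it says "Forest plots will be presented to summarize the results". It adds: "The subgroup categories may be combined if there is not enough representation of a specific subpopulation or if the statistical model fails to converge".

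The primary model is in SAP 5.3.3. It "will include the categorical treatment groups as interaction terms with time", and the stratification factors enter as main effects only. The treatment effect is the single coefficient β_x, for which "the 95% CI and p-value for crenezumab treatment effect will be presented".

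The exploratory objectives (Protocol 2.4; SAP Table 1) include the influence of a person's APOE ε4 "carrier status on the active treatment's cognitive, clinical, and adverse effects". They also include the predictive utility of baseline characteristics. Neither document gives a heterogeneity test or a between-level contrast for these subgroups.

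**The concern.** Whether crenezumab works differently by APOE4 or amyloid status is a question about the difference between two values of β_x. A model with one β_x cannot supply that difference. Fitting the model within each level gives two values, but the SAP asks for no contrast between them and no interval for it. The word separately does not appear in 5.3.5.1. Per-level fitting is nevertheless the natural reading, because levels may be merged when they are sparse or when the model fails to converge.

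Five factors, two levels and two endpoints give up to 5 × 2 × 2 = 20 estimates, each from part of the carrier cohort. The risk is that one bar excluding zero beside another that crosses it is taken as effect modification. Amyloid status is the likeliest place for this. Protocol 3.2.2 reports about half of carriers as amyloid-negative at baseline, in the passage explaining why this trial continued after the Phase III studies stopped.

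**Working it through.** **Inputs.**
- Protocol 4.10.8 and SAP 3: 30% reduction, placebo CV 65%, 25% dropout, 100 per arm, "two-sided testing at an overall 0.05 level". The standardised effect is 0.30/0.65 = 0.4615.
- SAP Appendix 2: 84 carriers per arm in the simulation built to resemble this study. Applying the 25% dropout to it (84 × 0.75 = 63) is my assumption.
- Subgroup splits: only amyloid status is documented, at about 50/50. All other splits below are assumed.
- A change-score test stands in for the slope model, because the documents give no variance inputs for the latter.

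**The plan's own figure.** With 100 × 0.75 = 75 per arm, z = 0.4615 × √(75/2) = 2.83. Power is Φ(2.83 − 1.96) = 80.7%, against the stated minimum of 80%. It reproduces. With 63 per arm, z = 0.4615 × √(63/2) = 2.59.

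**Same 30% effect in everyone.** For a level holding share s of n per arm, power is p = Φ(0.4615 × √(ns/2) − 1.96). The chance that exactly one of two levels is significant is p₁(1 − p₂) + p₂(1 − p₁).

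| Evaluable per arm | Split | p₁ / p₂ | Exactly one p<0.05 |
|---|---|---|---|
| 75 | 50/50 | 0.515 / 0.515 | 50.0% |
| 75 | 70/30 (assumed) | 0.657 / 0.340 | 55.0% |
| 75 | 90/10 (assumed) | 0.765 / 0.143 | 68.9% |
| 63 | 50/50 | 0.449 / 0.449 | 49.5% |
| 63 | 70/30 (assumed) | 0.582 / 0.294 | 53.4% |
| 63 | 90/10 (assumed) | 0.691 / 0.127 | 64.2% |

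For two equal levels the formula is 2p(1 − p), which cannot exceed 50%.

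**Sensitivity, 75 per arm, 50/50 split.**
- At alpha 0.04 the share is 49.9%. At 0.01 it is 40.5% (35.2% with 63 per arm).
- By true uniform effect, at alpha 0.05: 18% for a 10% reduction, 39% for 20%, 37% for 40% and 16% for 50%.
- By overall result, at alpha 0.05: 57% if it is significant, 21% if not.

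**Across five factors, assumed independent (simulation).** At least one factor is discordant in 84% of trials (75 per arm, all 50/50), 83% (63 per arm, all 50/50) or 87% (63 per arm, shares 0.5, 0.5, 0.3, 0.15 and 0.5). On average about 2.5 of the five are discordant.

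**With an interaction test.** Under a uniform effect, each factor gives a false signal 5% of the time at any split. For five independent tests, at least one signals in 1 − 0.95⁵ = 23%.

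For a 50/50 split, the between-level difference has SE = 0.65 × √(8/n) in units of the placebo decline:
- 75 per arm: SE 0.212, 95% CI half-width 42 percentage points of relative reduction. Power for a difference as large as the whole effect is Φ(0.30/0.212 − 1.96) = 29%.
- 63 per arm: SE 0.232, half-width 45 points, power 25%.

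**The case against.** The SAP sets no rule for judging subgroups by significance. The subgroups are supplementary, outside the formal testing procedure, and shown as forest plots in which intervals can be compared. The section has no reporting sentence of its own for p-values; they follow only from reuse of the primary analysis. If levels are fitted separately they hold different participants, so a reader can combine two estimates and standard errors into an approximate difference. All of this stands. It limits the point to an unstated contrast, not a wrong analysis.

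A reader might infer that the plan cannot answer the APOE4 objective. The documents do not support that. SAP 5.5.4 lists outcomes by APOE genotype, and in relation to baseline characteristics, and refers to a biomarker analysis plan that is not available here. Still, 5.3.5.1 fixes the subgroup method for the primary endpoints and defers only the amyloid threshold.

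The calculation is also a proxy. The planned model uses all observations, including partial data from dropouts and data after Week 260. The 84 per arm is a simulation setting, not an enrolment count. Independence of the five factors is doubtful: Protocol 3.2.3 puts the start of amyloid accumulation at around age 30, which ties amyloid status to age.

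Finally, the interaction test is weak. That is a reason to print the wide interval, not to leave it out.

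**Conclusion.** The gap is real but modest. SAP 5.3.5.1 specifies no treatment-by-subgroup-by-time term and no between-level difference with an interval, so its stated output does not directly estimate effect modification. At the design effect, a uniform benefit looks present in one level and absent in the other in about half of trials for a balanced factor (49 to 50%), against 5% false signals from an interaction test. For at least one of five factors, the comparison is roughly 83 to 87% against 23%, assuming independence.

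Two stronger readings go too far:
- That a uniform effect will usually split in this way for a given factor. For equal levels the unconditional share cannot pass 50%. It does so only with unequal splits, which the documents do not give, or after a significant overall result. It falls at the 0.01 level first assigned to FCSRT ("The type I error is split between testing the treatment effect on the API ADAD Composite Cognitive Test total score" and the Cueing Index, SAP 2), or if the true effect is clearly smaller or larger than 30%.
- That the planned output will mostly produce false subgroup conclusions. That needs a significance-based reading the SAP does not prescribe.

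The primary inference is untouched. This is an inexpensive improvement.

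**What to change.** In SAP 5.3.5.1, for each factor and endpoint, fit one random coefficient model in all mITT carriers. Include subgroup, subgroup-by-time, treatment-by-time and treatment-by-subgroup-by-time terms, and keep the stratification factors and random effects of 5.3.3. With G the subgroup indicator, the slope part becomes (β + β_G G + β_x I_x + β_xG I_x G + u₁)t. The level-specific effects are β_x and β_x + β_xG, and their difference is β_xG.

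Show both effects in the forest plot, together with β_xG, its 95% CI and the interaction p-value. Label all subgroup results descriptive. State that any comment on effect modification rests on β_xG alone, and that a non-significant interaction does not show homogeneity, given power of about 25 to 29% even for a difference as large as the whole effect.

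The single model assumes common variance components across levels. Where that is doubtful, the difference of the two separate estimates, with SE = √(SE₁² + SE₂²), is a simple check.

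The cost is SAP wording and minor programming. No new data are needed.
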